Evinacumab (REGN1500) is a human IgG4 monoclonal antibody specific for ANGPTL3 and is being developed for treatment of dyslipidemia including hypertriglyceridemia (HTG) and hypercholesterolemia. Evinacumab has been studied in approximately 100 individuals with elevations in LDL-C and TG and has been generally well tolerated up to single doses of 20 mg/kg intravenous (IV), and in multiple subcutaneous (SC) doses up to 450 mg administered weekly and

20 mg/kg IV administered every 4 weeks for approximately 8 weeks. After single doses, evinacumab lowered TG up to ~80% in participants with TG <1000 mg/dL and lowered LDL-C up to 27% in participants with TG <500 mg/dL. In a multiple ascending dose study, evinacumab robustly lowered TG (up to ~72%) and LDL-C (up to ~34%) in patients with TG (150 – 500 mg/dL) and LDL-C >100 mg/dL and had a long durability of treatment effect. However, TG lowering was highly variable in a small cohort of patients with TG \geq 1000 mg/dL given a single dose of evinacumab (4 patients received 250 mg SC and 2 patients received 20 mg/kg IV). Although certain individuals exhibited the rapid and substantial lowering of TG (up to 90%), some of the patients with underlying LPL and other mutations did not show robust lowering following single doses of evinacumab. The reason for the mixed response was not clear. Three out of the 6 patients treated with evinacumab and 1 placebo-treated patient in the cohort of patients with baseline TG \geq 1000 mg/dL had an occurrence of acute pancreatitis during the study. These serious adverse events (SAEs) were not considered related to evinacumab since all of the patients had a history of prior pancreatitis episodes, had other underlying etiologies, and the events occurred 70 days or later after the single dose of antibody when antibody levels were low or undetectable.

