7. STUDY TREATMENTS

7.1. Investigational and Reference Treatments

Sterile evinacumab drug product will be provided in a 20 mL single-use glass vial at a concentration of 150 mg/mL.

Double-Blind Treatment Period: Patients will be randomized to receive either evinacumab 15 mg/kg or matching placebo administered IV every 4 weeks (± 4 days) on days 1, 29, and 57.

Single-Blind Treatment Period: All patients will receive evinacumab administered IV at a dose of 15 mg/kg every 4 weeks (± 4 days) on days 85, 113, and 141.

Instructions on management of infusion reactions are provided in Section 7.5.

Instructions on dose preparation are provided in the pharmacy manual.

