4.8.1. Adverse Events Variables

The period of safety observation starts from the time when the patient gives informed consent and continues into the following periods:

- The PRE-TREATMENT period is defined from the day the ICF is signed to the day before the first dose of double-blind study treatment administration.
- The double-blind treatment-emergent adverse event (TEAE) period is defined from the day of the first dose of double-blind study treatment administration to the day of the last dose of double-blind study treatment administration + 168 days (24 weeks) for those patients not proceeding into the SBTP, or up to the day before the first dose of single-blind study treatment administration for those patients proceeding into the SBTP.
- The single-blind treatment-emergent adverse event (TEAE) period is defined from the day of the first single-blind study treatment administration to the day of the last single-blind study treatment administration + 168 days (24 weeks).
- The POST-TREATMENT period is defined from the day after the end of the respective TEAE periods to the last study visit.

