5.8.3. Analysis of Incidence of Recurrent Acute Pancreatitis

Acute pancreatitis event incidence table will present the number (n) and percentage (%) of patients experiencing such event. Multiple occurrences of the same event in the same patient will be counted only once in the tables within a treatment phase (TEAE or post-treatment AE). The denominator for computation of percentages is the respective safety analysis set within each treatment group.

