5.8.5. Clinical Laboratory Measurements

For respective treatment period (DBTP and SBTP), clinical laboratory parameter actual values (quantitative) and change from baseline values will be descriptively summarized at baseline and each post-baseline visit (collected up to the day of last dose of study treatment +28 days) by at least patient number, mean, median, Q1, Q3, SD, minimum and maximum. Clinical laboratory parameters mean changes from baseline, with the corresponding SE, can be plotted at each visit in the case results warrant further investigation. These parameters will be presented by the biological functions defined in Section 4.8.2. For glucose, only fasting samples will be included in the summaries.

Individual patient laboratory parameter measurements will be additionally evaluated by PCSV criteria (See [Appendix 10.3](#)), specifically identifying patients with at least one post-baseline

measurement that meets the PCSV criteria within the respective TEAE periods. These laboratory parameters will be presented by the biological functions defined in Section 4.8.2. The incidence of PCSVs at any time during the respective TEAE periods will be summarized regardless of the baseline level, and again according to the following baseline categories:

- Normal (according to PCSV criterion/criteria)/missing
- Abnormal according to PCSV criterion or criteria

Patient listings of laboratory measurements that meet PCSV criteria will be provided for the report appendix. For those laboratory parameters that don't have an associated PCSV criteria, similar summary tables can be provided based on measurements outside the central laboratory normal ranges, if applicable.

Drug-induced liver injury

For respective treatment period (DBTP and SBTP), an evaluation of drug-induced serious hepatotoxicity (eDISH) with the graph of distribution of peak values of ALT versus peak values of total bilirubin will also be presented using post-baseline values during respective TEAE periods. Note that the ALT and total bilirubin values are presented on a logarithmic scale. The graph will be divided into 4 quadrants with a vertical line corresponding to 3 x ULN for ALT and a horizontal line corresponding to 2 x ULN for total bilirubin.

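### The pancreatitis and hospitalisation tables merge on-treatment with off-drug time in the single-blind period, and count double-blind non-continuers over a longer window than continuers

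*SAP*

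**What the plan says.** SAP 4.8.1 defines the windows. The single-blind window starts at the first single-blind dose and runs "to the day of the last single-blind study treatment administration + 168 days (24 weeks"). The double-blind window runs "up to the day before the first dose of single-blind study treatment administration for those patients proceeding into the SBTP", but "to the day of the last dose of double-blind study treatment administration + 168 days (24 weeks) for those patients not proceeding into the SBTP". The post-treatment period runs "from the day after the end of the respective TEAE periods to the last study visit".

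SAP 5.8.3 reports pancreatitis as the number and percentage of patients. Repeat events in one patient "will be counted only once in the tables within a treatment phase (TEAE or post-treatment AE"), and the denominator is the safety set in each treatment group. SAP 5.8.4 does the same for hospitalisations, and SAP 5.8.1 plans tables of post-treatment AEs and SAEs. For these events the SAP plans no patient-time, no time-to-event analysis and no split by time since last dose.

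Elsewhere the SAP uses a shorter interval. Exposure duration (4.6) adds 28 days to the last dose, and the by-visit laboratory summaries use values "collected up to the day of last dose of study treatment +28 days", as do the vital signs (5.8.6). Protocol 5.1 calls day 170 to day 309 the off-drug follow-up period.

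**The concern.** The SAP's counting rule separates a treatment-emergent phase from a post-treatment phase, but its window definition leaves almost nothing in the second. A patient with one event during dosing and another months after the last dose appears once, and the reader cannot tell when the events fell.

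This matters more here than for adverse events in general. Protocol 10.2 and SAP 2.2 put the number needed for triglycerides at about 30, and justify going to about 50 by the wish to explore an effect on pancreatitis. Comparing evinacumab with placebo on recurrent pancreatitis is an exploratory objective (Protocol 2.3, SAP 1.2.3). Event timing is also a live question: in the earlier cohort described in the protocol's Introduction, "events occurred 70 days or later after the single dose of antibody when antibody levels were low or undetectable".

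A second problem affects the randomised comparison. A patient who stops during the double-blind period stays at risk in that table two to nearly three times as long as one who continues, and most of the extra time is off treatment. If non-continuation differs by arm, the crude percentages differ for that reason alone.

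**Working it through.** **Inputs.** Double-blind doses on days 1, 29 and 57; single-blind doses "on days 85, 113, and 141" (Protocol 7.1); dose visits ±4 days and last visit on day 309 ±5 days (Schedule of Events); the 168-day extension (SAP 4.8.1); the 28-day convention (SAP 4.6, 5.8.5, 5.8.6). Days are counted inclusively.

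**1. End of the single-blind window.** 141 + 168 = day 309. This equals the end of study stated in Protocol 5.1 and SAP 2.3.

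**2. Post-treatment phase, fully dosed patient.** Nominally 309 − 309 = 0 days. The longest case within the visit windows has the last dose on day 137 and the last visit on day 314: 314 − (137 + 168) = 9 days.

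**3. Composition of the single-blind window.**
- Whole window, day 85 to 309: 309 − 85 + 1 = 225 days.
- To last dose + 28, day 85 to 169: 85 days.
- Remainder, day 170 to 309: 140 days; 140/225 = 62.2%.
- Moving the first and last doses within ±4 days gives 60.1% to 64.5%.

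**4. Dependence on the cut-point.** The share of the window after an assumed on-drug tail of T days is (168 − T)/225:

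| T (days) | Days after | Share |
|---|---|---|
| 28 | 140 | 62.2% |
| 42 | 126 | 56.0% |
| 55 | 113 | 50.2% |
| 56 | 112 | 49.8% |
| 70 | 98 | 43.6% |

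The later part is the larger one only if T is 55 days or less.

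**5. What one total conceals.** Take a constant event rate over all 225 days, and compare it with half that rate for 85 days followed by r times that rate for 140 days. The totals are equal when 0.5 × 85 + 140r = 225, so r = 182.5/140 = 1.30. The planned table cannot distinguish these two time courses, whatever the underlying rate.

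**6. Double-blind windows.** Continuers: day 1 to 84 = 84 days. Non-continuers, by last dose:

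| Last dose | Window (days) | Ratio to 84 | Share after last dose + 28 |
|---|---|---|---|
| Day 1 | 169 | 2.0 | 140/169 = 83% |
| Day 29 | 197 | 2.3 | 140/197 = 71% |
| Day 57 | 225 | 2.7 | 140/225 = 62% |

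**7. Possible size in the randomised comparison.** The documents give no pancreatitis rate, so one is assumed. Risk over d days is 1 − exp(−rate × d/365.25). The last column is an extreme case with no drug effect: 20% of one arm does not continue (all with last dose on day 57) and nobody in the other arm stops. The spurious difference is then 0.2 × (225-day risk − 84-day risk).

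| Assumed rate per patient-year | 84 days | 225 days | Spurious difference |
|---|---|---|---|
| 0.1 | 2.3% | 6.0% | 0.7 points |
| 0.2 | 4.5% | 11.6% | 1.4 points |
| 0.4 | 8.8% | 21.8% | 2.6 points |

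For scale, 50 patients at 2:1 gives a placebo arm of about 17, where one patient is 1/17 = 5.9 points.

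**8. Can a fixed window be filled?** Protocol 7.4.2 and 8.1.2 follow patients who stop early for at least 24 weeks after the last dose. The earliest case is 1 + 168 = day 169, beyond day 84. The data are planned to exist.

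**The case against.** The strongest reply is that the randomised comparison is largely sound. Only the double-blind period has a placebo arm, it is tabulated separately, and for patients who continue it is 84 days on assigned treatment with no tail. That stands. The 168-day extension enters only through non-continuers, and the only related figure in the documents is an assumed 20% dropout that is not specific to this period. A reader might infer that the comparison as a whole is compromised; the documents do not support that.

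A reader might also infer that splitting the single-blind table would show protection on drug or relapse after withdrawal. It would not. Everyone receives evinacumab in that period, so there is no concurrent control. Nor do the earlier cases establish withdrawal relapse: the Introduction reports one in a placebo patient and attributes the cases to previous pancreatitis and other causes.

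It can further be said that the information is not lost. Pancreatitis has its own tick box and detail page (SAP 4.8.1.2, 4.8.1.4), onset timing is needed to assign events to periods, and serious events are listed by patient. That too stands: the gap is in the planned summaries, not in the data.

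The long window is no slip either. Protocol 10.4.5.1 runs the safety treatment period to the end of study, and Protocol 10.4.3.1 expects carryover into follow-up. So 28 days is the dosing interval and not a proven end of effect, and calling most of the window off-drug depends on the assumed tail. Finally, the post-treatment phase is not empty for everyone, because some patients may be followed longer (Protocol 7.4.2, 8.2.6.2).

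What remains is a phase split that separates almost nothing for fully dosed patients, and unequal windows inside one percentage.

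**Conclusion.** The point holds in a limited form. For patients dosed on schedule, the post-treatment phase is nominally 0 days and at most 9. The single-blind pancreatitis and hospitalisation tables merge 85 days with 140 days that the protocol itself labels off-drug (62%; 43.6% if an assumed 70-day tail counts as on-drug). In the double-blind tables, non-continuers contribute 169 to 225 days against 84 for continuers.

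The effect on the randomised comparison is confined to double-blind non-continuers. Under the assumed rates of 0.1 to 0.4 per patient-year and an extreme imbalance, it is 0.7 to 2.6 percentage points, less than one patient in the placebo arm. The endpoint is exploratory and the summaries descriptive. The change is still worth making before unblinding: it costs little, it avoids choosing a split after seeing the events, and it concerns the outcome used to justify the larger sample.

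The day counts use nominal visits and full dosing unless stated; the event rates, the imbalance and the tails beyond 28 days are illustrations.

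**What to change.** For pancreatitis and hospitalisations only:

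1. **Randomised comparison.** Count events for every treated patient from day 1 to the day before the first single-blind dose, or to day 84 for those who do not continue, regardless of discontinuation. Give events per patient-time as support, which also absorbs the ±4-day variation in the first single-blind dose. Ending the window at last dose + 28 days for early stoppers would make the windows unequal again and drop events after stopping.
2. **Single-blind tables.** Split at last dose + 28 days, which matches the SAP's exposure, laboratory and vital-sign convention and the protocol's off-drug start on day 170. Show on-treatment and follow-up columns with patient-time, and count a patient in each column where an event occurs. Add one later, prespecified cut-point as sensitivity, because carryover is expected.
3. **Wording.** State that the split describes event timing in an uncontrolled period and is not evidence of protection or of withdrawal relapse.

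Keep the 168-day window for the general TEAE tables. No new data or design change is needed. The cost is a few extra tables and a short SAP amendment.

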4.8.1.1. Adverse Events and Serious Adverse Events

Adverse events (including serious adverse events (SAE), AEs leading to treatment discontinuation, deaths, and AEs of special interest) are recorded from the time of signed informed consent until the end of study. All AEs identified by the Investigator will be reported and described.

All AEs will be coded by “lowest level term (LLT)”, “preferred term (PT)”, “high level term (HLT)”, “high level group term (HLGT)” and associated primary “system organ class (SOC)” using the version of MedDRA in effect at the time of the first database lock.

Adverse Event Observation Period

- Pre-treatment AEs are AEs that developed or worsened or became serious during the pre-treatment period.
- Double-blind and single-blind TEAEs are AEs that developed or worsened or became serious during the respective TEAE periods.
- Post-treatment AEs are AEs that developed or worsened or became serious during the post-treatment period.

4.8.1.2. Adverse Events of Special Interest

Adverse events of special interest (AESI) are AEs (serious or non-serious) required to be monitored, documented, and managed in a pre-specified manner. AESIs will be recorded on the adverse event e-CRF using dedicated tick boxes, and/or identified using standard MedDRA queries (SMQ), and/or company MedDRA queries (CMQ), and/or applicable laboratory assessments. [Appendix 10.2](#) contains the definitions used to identify AESIs:

The AESIs include the following:

- Anaphylactic reactions (CRF)
- General allergic events (SMQ)

- Infusion reactions (CRF)
- Pregnancy (CRF)
- Symptomatic overdose with investigational medicinal product (CRF)
- Neurocognitive events (CMQ)
- New onset of diabetes (NOD) (lab data)
- Pancreatitis (CRF)

4.8.1.3. Events Causing Death

The observation periods for patient deaths are per the observation periods defined above.

- Death on-treatment: deaths occurring during the respective TEAE period (double-blind or single-blind),
- Death post-treatment: deaths occurring during the post-treatment period.

4.8.1.4. Incidence of Recurrent Acute Pancreatitis

Acute pancreatitis events are recorded in e-CRF as an AESI with event details captured in the complimentary e-CRF page.

4.8.1.5. Hospitalizations

Hospitalizations for abdominal pain, hospitalizations for pancreatitis, and hospitalizations for cardiovascular disease are recorded in AE e-CRF.

4.8.2. Laboratory Safety Variables

Clinical laboratory tests will consist of blood analyses (including hematology, clinical chemistry and other) and urinalysis. Clinical laboratory values will be converted and analyzed in both international units and US conventional units, with associated normal ranges provided by the central laboratory. Both actual test values and “change from baseline” values (defined as the post-baseline value minus the baseline value) will be used in the result summaries. Potentially clinically significant values (PCSV) ranges will be applied to the laboratory test values as applicable (see [Appendix 10.3](#) for PCSV definitions). For those laboratory tests that do not have PCSV ranges, central laboratory normal ranges will be applied to identify out-of-range values. All laboratory test samples will be collected before study treatment administration during the protocol scheduled visits.

In addition, local laboratory tests for hematology will be summarized in the same manner as the central lab results.

The laboratory parameters will be classified as follows:

Hematology:

- Red blood cells and platelets: hemoglobin, hematocrit, erythrocytes count, red blood cells, platelets count, reticulocyte count, red blood indices

- White blood cells: white blood cells, neutrophils, lymphocytes, monocytes, basophils, eosinophils

Clinical chemistry:

- Metabolism: glucose, total protein, albumin, creatine phosphokinase
- Electrolytes: sodium, potassium, chloride, calcium, bicarbonate
- Renal function: creatinine, blood urea nitrogen (BUN), uric acid
- Liver function: ALT, aspartate aminotransferases (AST), alkaline phosphatase (ALP), total bilirubin, LDH

Urinalysis

Urinalysis will include the following parameters: color, clarity, pH, specific gravity, ketones, protein, glucose, blood, bilirubin, leukocyte esterase, nitrite, WBC, RBC, hyaline and other casts, bacteria, epithelial cells, crystals, and yeast.

4.8.3. Vital Signs

Vital signs parameters will include weight (kg), heart rate (bpm), respiration (rpm), temperature (C or F), systolic and diastolic blood pressure (mmHg) after resting at least five minutes. Both actual test values and “change from baseline” values (defined as the post-baseline value minus the baseline value) will be provided for protocol specified visits. Potentially clinically significant values (PCSV) ranges will be applied to the vital sign parameter values as applicable (see [Appendix 10.3](#) for PCSV definitions).

4.8.4. 12-Lead Electrocardiography (ECG)

Electrocardiograms will be recorded in the supine position after the patient has rested for at least 10 min. Electrocardiogram assessments will be described as normal or abnormal.

4.8.5. Physical Examination Variables

Physical examination will be conducted at the protocol scheduled visits (See [Appendix 10.4](#) for schedule of event). The result is an outcome of clinically significant (Yes/No, not examined).

4.9. Pharmacokinetic Variables

Pharmacokinetic (PK) variables include total evinacumab and total ANGPTL3 concentrations at each time point specified in the protocol (See [Appendix 10.4](#) for schedule of event).

4.10. Anti-Drug (evinacumab) Antibody Variables (ADA)

Anti-drug antibody variables will include ADA status (positive or negative), titer and neutralizing antibody (NAb) status for samples analyzed at each time point specified in the protocol (See [Appendix 10.4](#) for schedule of event).

4.11. PRO Variables

The baseline value is defined as the last available measurement prior to the date of the first double-blind study treatment administration (applicable to measurement derivations during both DBTP and SBTP).

The patient experience of symptoms and the impact on dietary behavior will be assessed with two de novo PRO measures: the Hypertriglyceridemia and Acute Pancreatitis Symptoms Scale (HAP-SS) and the Hypertriglyceridemia and Acute Pancreatitis Dietary Behavior questionnaire (HAP-DB).

- Hypertriglyceridemia and Acute Pancreatitis Symptom Scale (HAP-SS)

The HAP-SS is a 19-item measure of symptoms that has a 24-hour recall period. Four pain items are captured on a 0-10-point severity NRS, each scored 0='No pain' to 10='Worst possible pain', while the 15 non-pain items are captured on a 5-point frequency Likert scale, each scored from 1='None of the time' to 5='All of the time'. The proposed structure of the measure is currently being tested and is yet to be finalized but currently consists of a total score and four domain scores: pain; abdominal symptoms; physical symptoms; other symptoms, each scored 0 (no symptoms) to 100 (severe symptoms).

The Pain domain includes the four items: item 1 - stomach pain average, item 2 - stomach pain at worst, item 3 - back pain at worst, item 4 - stomach pain after eating (possible score range: 0 to 40).

The Abdominal symptoms domain includes the 6 items: item 5 – bloated or swollen stomach, item 6 – nausea/feeling sick, item 7 – vomiting, item 8 – passed excessive gas, item 9 – loose stools/diarrhoea, item 10 – foul smelling, light-coloured or greasy stool (possible score range: 6 to 30).

The Physical symptoms domain includes 5 items: item 11 – fever or flu like symptoms, item 12 - insomnia, item 13 – excessive sweating, item 14 – dizziness (lightheadedness), item 15 - racing heart rate (felt like your heart was racing) (possible score range 5 to 25).

The Other symptoms domain includes 4 items: item 16 – fatigue, item 17 – loss of appetite, item 18 – been hungry after eating, item 19 – felt full after eating a small amount (possible score range 4 to 20).

Each item will be calculated at each evaluation/visit as the mean of the item scores over the seven days previous to the visit; each domain score at each evaluation/visit will be calculated as the sum of the mean component item scores. Each domain score will then be transformed onto a 0-100 scale, with the total score being the sum of the four domain scores (0-400), also then transformed to a 0-100 scale.

To transform to a 0-100 scale the following algorithm will be applied:

Transformed score = $100 \times (\text{score} - \text{minimum possible score}) / (\text{maximum} - \text{minimum possible score})$.

- Dietary behavior questionnaire (HAP-DB)

The HAP-DB is a 6-item measure of dietary behavior that has a 24-hour recall period. The items in the measure are all captured on a 5-point frequency Likert scale, each scored from 1='None of

the time' to 5='All of the time'. The proposed structure of the measure is currently being tested and is yet to be finalized but currently consists of a dietary impact total score, ranging from 6 (no impact) to 30 (severe impact).

The six HAP-DB items are: item 1 – amount of food eaten, item 2 – fatty or greasy food, item 3 – carbohydrates, item 4 – sugar or sugary foods, item 5 – alcohol intake, item 6 – skipped meal.

Each item will be calculated at each evaluation/visit as the mean of the item scores over the seven days previous to the visit. The total score will be calculated as the sum of the six item scores and then transformed to a 0-100 score.

To transform to a 0-100 scale the following algorithm will be applied:

Transformed score = $100 \times (\text{score} - \text{minimum possible score}) / (\text{maximum} - \text{minimum possible score})$.

4.11.1. Number of pain and abdominal symptom free days and days where meals are avoided

Exploratory endpoints of the frequency of stomach pain (on average, and at its worse), pain (stomach pain, back pain, stomach pain at its worst after eating), and abdominal symptom free days at each evaluation/visit will be defined as the number and percentage of stomach pain free days, number and percentage of pain free days, and the number and percentage of abdominal symptom free days over the seven days prior to the visit, as assessed by the HAP-SS:

- A stomach pain free day will be determined if the patient scores 0 - 'No Pain' on both of the HAP-SS stomach pain items 1 and 2.
- A pain free day will be determined if the patient scores 0 - 'No Pain' on all of the HAP-SS pain items 1, 2, 3 and 4.
- An abdominal symptom free day will be determined if the patient scores 1 - 'None of the time' to all the HAP-SS abdominal symptoms items 5-10.

An additional exploratory endpoint of the number of days where meals are avoided will be assessed as the number of days where all meals are skipped as assessed by the HAP-DB:

- A day where all meals are avoided will be determined if the patient scores 5 - 'All of the time' to item 6 in HAP-DB, skipped meals.

